9.6 Data Analyses

We will follow the CONSORT Statement guideline to analyze and report the data from this trial: <http://www.consort-statement.org/consort-statement/>. The primary analyses will be the ITT population, that is, patient intervention status will be analyzed as randomized. As a secondary analytic goal, we will also consider per protocol analysis. Primary hypothesis: *Asthma control as assessed by the Asthma Control Questionnaire will improve more in MBSR than in HLC participants at 18-month follow-up.* We will first analyze the data descriptively by study arm (intervention vs. control) and by time point (e.g., 18 month), report descriptive statistics (mean, SD, lower and upper quartiles, median and range), and test between arm differences using t-test (normally distributed outcomes), Wilcoxon rank sum test (for skewed variables) and Chi2 test statistics (categorical variables, such as occurrence of symptoms). We will carefully examine the distributional characteristics of the outcome variables to identify proper distributional function or statistical transformations for further modeling.

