Since the measures are longitudinal, we will also use linear or generalized mixed models to evaluate the intervention effects on ACQ score and presence of symptoms. We will include intervention indicator (MBSR=1 and HLC control=0) in the mixed models to estimate intervention effect. To account for auto-correlations among repeated measures on the same patient, we will include in the mixed models patient level random effects and use either first order autoregressive correlation or unstructured covariance structure for robust estimates. Within physician correlations will be modeled by including physician level random effects. We will also consider inclusion of key physician attributes such as sub-specialty in the models in order to understand how physician factors may influence the intervention effects. Since interventions will be delivered by class, we will model each class as a potential random effect in the model and test if inclusion of the class level random effect improves model estimation. If class level random effect exists, we will fit a two level hierarchical model (repeated measures on patients nested within each class). We will estimate the intervention effects with and without adjusting for patient socio-demographic and clinical co-variables. Covariate adjustments will focus co-variables that are unbalanced between the two arms, or inclusion of them will lead to substantial reduction of

variance in estimates of intervention effects, or those modifying the intervention effects. To test whether intervention effects vary by these factors, we will test the significance of the interactions between intervention indicators and each co-variable. A significant interaction term signals potential variation of intervention effect, which warrants further investigation.

To model presence of any specific component of asthma control at follow-up time points, we will use mixed effects logistic regression models. This analysis is important to understanding whether specific control component worked well or not among patients, and if there is any differential effect between the two arms. To model intervention effects on number of symptoms at each follow-up, we will use mixed effects Poisson regression models. General modeling approaches are similar to those for ACQ scores and thus not repeated, except that the underlying statistical distributions differ.

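### Section 9.6 does not tie the 18-month ACQ hypothesis to one analysis: no 18-month contrast is specified, baseline ACQ is optional, and adjusted and unadjusted results are unranked

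*Combined protocol and SAP*

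**What the plan says.** Sections 1.1, 9.5.1 and 9.6 place the primary hypothesis at 18 months. In 9.6 it reads "Asthma control as assessed by the Asthma Control Questionnaire will improve more in MBSR than in HLC participants at 18-month follow-up".

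Section 9.6 then lists these analyses:

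- **Descriptive step.** "We will first analyze the data descriptively by study arm" and time point, and within that step "test between arm differences using t-test (normally distributed outcomes), Wilcoxon rank sum test (for skewed variables"). The choice between them depends on the observed distribution, and transformations are also left open.
- **Mixed models.** Because the data are longitudinal, "we will also use linear or generalized mixed models to evaluate the intervention effects on ACQ score". The only fixed effect committed to is arm: "We will include intervention indicator (MBSR=1 and HLC control=0) in the mixed models to estimate intervention effect". Visit, arm-by-visit and baseline ACQ are not named. The only interactions named are between arm and covariates.
- **Covariance.** The plan will "use either first order autoregressive correlation or unstructured covariance structure for robust estimates". Physician random effects are planned.
- **Adjustment.** "We will estimate the intervention effects with and without adjusting for patient socio-demographic and clinical co-variables". On selection: "Covariate adjustments will focus co-variables that are unbalanced between the two arms", or that reduce the variance of the estimated effect substantially, or that modify the effect. Site and severity, the stratification factors, are not listed as model terms.

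The only element that 9.6 fixes as primary is the intention-to-treat population.

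Section 9.2 sizes the trial for 0.25 ACQ points by analysis of covariance or, alternatively, a linear mixed model, with one baseline and three follow-up measures. Its assumed means and SD are for the average of the three follow-ups.

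**The concern.** A time-specific hypothesis needs a time-specific contrast. A mixed model whose only stated fixed effect is arm estimates an effect pooled over the visits in the model, not the effect at 18 months. A t-test or Wilcoxon test at 18 months does address the stated time point, but 9.6 places it in a descriptive step and offers it alongside the mixed models.

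Two things are at stake. The first is precision. ACQ is measured at baseline in everyone and is correlated with later ACQ, yet its inclusion depends on what the trial data show. The second is that the result readers take as primary is not fixed in advance. Adjusted and unadjusted estimates, two covariance structures and two families of test all remain open, with no ranking.

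**Working it through.** **Inputs** (section 9.2): 108 per arm; difference 0.25 (1.24 against 1.49); SD 0.66; within-patient correlation r = 0.45; within-physician correlation 0.05; 12 physicians at each of two sites with 9 patients each; 5% level. Assumptions: two-sided test (9.2 does not say), normal approximation, equal correlation between all visits.

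**1. Physician design effect.** Patients are randomized individually, so each physician's patients are spread over both arms. With 9 of a site's 108 patients per physician and 1:1 allocation within site, the expected design effect for the arm difference is (1 − 0.05) + 0.05 × (108 − 9)/(108 − 1) = 0.95 + 0.05 × 0.925 = 0.996. Simulating 20,000 allocations gave a mean of 0.996 and a 95% range of 0.974 to 1.026. A value of 1.0 is used below.

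**2. The plan's own figure.** For a baseline-adjusted three-visit mean, the variance factor is (1 + 2r)/3 − r² = 0.6333 − 0.2025 = 0.4308.
- If 0.66 is the SD at one visit: SE = 0.66 × √(2 × 0.4308/108) = 0.0590; z = 0.25/0.0590 = 4.24; power 98.9%.
- If 0.66 is the SD of the three-visit average: the single-visit SD is 0.66/√0.6333 = 0.829; SE = 0.0741; z = 3.37; power 92.1%.

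The statement of at least 80% power holds either way for the averaged, baseline-adjusted analysis. The question is what happens at 18 months.

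**3. The 18-month contrast, without and with baseline ACQ.** The unadjusted SE is SD × √(2/108). With baseline it is multiplied by √(1 − 0.45²) = √0.7975 = 0.893. Power is Φ(0.25/SE − 1.96).

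| SD at 18 months | Baseline ACQ | SE | z | Power |
|---|---|---|---|---|
| 0.66 | ignored | 0.0898 | 2.78 | 79.5% |
| 0.66 | included | 0.0802 | 3.12 | 87.6% |
| 0.829 | ignored | 0.1129 | 2.22 | 60.1% |
| 0.829 | included | 0.1008 | 2.48 | 69.9% |

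Including baseline cuts the SE by 1 − 0.893 = 11%. Omitting it widens the SE by 1/0.893 − 1 = 12%, which is like having 108 × 0.7975 = 86 patients per arm.

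**4. Type I error.** Null trials were simulated with 108 per arm, r = 0.45 and normal data. The unadjusted and the baseline-adjusted 18-month tests each reject about 5% of the time. Reporting whichever has the smaller p-value gives about 7%. Adjusting for baseline only when it is significantly imbalanced gives about 4.5%.

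**The case against.** **Section 9.2 already implies a baseline-adjusted model.** It does point that way, and read with 9.2 the mixed model looks like the intended main analysis. But 9.2 is a sizing statement, offers two methods, and targets a three-visit average. It does not say what tests the 18-month hypothesis.

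**Visit-specific effects appear intended.** The descriptive tests are by time point, and 9.6 models symptom counts at each follow-up with an approach said to resemble that for ACQ. This is a fair reading of intent, but no term or contrast commits to it.

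**The 12% loss is one reading.** It compares analysis of covariance with a test that ignores baseline. If baseline ACQ were a response in the mixed model with visit-specific effects, or entered under the variance-reduction rule, some or all of the loss would disappear. This stands: the power gap in the table is what is at risk, not what the text makes certain.

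**Selective reporting is neither planned nor easy.** Section 6.2.3 blinds the statistician and investigators and keeps the arms coded A and B until the main analysis is done. That limits choosing the result that favours MBSR, though not choosing the smaller p-value. The plan nowhere proposes such a choice.

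**The covariate rule does no demonstrated harm to type I error.** This stands for adjustment on imbalance. The other two selection rules were not simulated. Leaving out site and severity is conservative.

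**Conclusion.** The specification gap is real and should be closed. Section 9.6 names no single analysis for the 18-month hypothesis and leaves the most useful covariate optional. Against a test that ignores baseline, the power at risk is 8.1 points (79.5% against 87.6%) or 9.8 points (60.1% against 69.9%), depending on which SD 0.66 represents. Both pairs assume r = 0.45, equal correlation between visits, 108 per arm, a two-sided 5% test and a physician design effect of about 1.0.

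A reader might infer three stronger conclusions that the documents do not support:

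- **Physician clustering makes the power much lower.** The familiar factor 1 + (9 − 1) × 0.05 = 1.40 would apply if each physician's patients all went to one arm. They are randomized individually, so it does not fit this design.
- **The primary test has a 7% error rate.** That figure requires choosing between the two results after seeing both. It shows why ranking matters; it does not describe what is planned.
- **Testing the class random effect before keeping it inflates the error by a known amount.** The documents give no within-class correlation, so no size can be stated.

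Nor does the point show that 9.2's power statement is wrong for the averaged analysis it describes.

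**What to change.** Add to section 9.6: *The primary analysis is a linear mixed model of ACQ at 6, 12 and 18 months, with arm, visit, arm-by-visit, baseline ACQ, site and asthma severity as fixed effects, an unstructured within-patient covariance, and a physician random effect. If the model does not converge, the covariance becomes first-order autoregressive with a patient random effect. The primary test is the 18-month arm contrast, two-sided 5%.* Label the t-test or Wilcoxon, transformed, unadjusted and other covariate-adjusted results as supportive. Say also what happens if the physician effect cannot be estimated, and whether the class effect belongs to the primary or a supportive model.

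This replaces a stated data-driven covariate rule with required terms. All the variables are already collected or used in randomization, so the change is to wording. It costs a few degrees of freedom.

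One consequence should be written down. The primary contrast is a single visit, whereas 9.2 was sized on a three-visit average. Section 9.2 should acknowledge this, say which SD 0.66 is, and give the power for the 18-month contrast.

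This wording does not settle how missing ACQ values are handled. Section 9.3 proposes multiple imputation for missed visits and dropouts, and 9.6 proposes inverse probability weighting for dropouts. That needs its own decision before the primary analysis is fully defined.

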9.2 Sample Size and Randomization

The trial size was determined based on hypothesized intervention effects on ACQ score, the primary outcome. We will recruit 254 individuals, but base power calculations on n=216 (108 per arm) anticipating $\leq 15\%$ loss to follow-up. With one baseline measure and 3 follow-up measures at 6, 12 and 18 months, the trial can detect an intervention effect of 0.25 ACQ score improvement using ANCOVA (or linear mixed models) method at 5% significance level and at least 80% power. This treatment effect is consistent with recent reported drug-trials for asthma control. Based on literature, for sample size estimation we assumed the mean (SD) of ACQ scores for the MBSR and HLC groups are 1.24 (0.66) and 1.49 (0.66) averaged over the three follow-up time points, respectively, and a serial correlation of 0.45 within patients. We expect to recruit patients from 12 physicians at each site, with on average each physician contributing 9 patients. Because within physician correlation has not been reported in literature and our small-sized pilot study does not allow an accurate estimation, we conservatively assumed a modest within physician correlation of 0.05. The sample size was estimated using Stata MP 12.

Our sample size estimation and power analysis are conservative and the treatment effect is chosen for other important reasons: a) to preserve the possibility of addressing treatment heterogeneity by select patient and physician characteristics (e.g. differential effects between male and female participants, ethnicity); we plan to conduct subgroup analysis and examine how treatment effects may differ. Such analysis will be very important when refining the treatment protocols and for dissemination if proved effective; b) other than the primary outcome, we are also interested in other primary/secondary outcomes described below and powered the trial to detect meaningful changes in these outcomes as well. The sample size is determined to allow us to achieve all these analytic goals, not just for the primary outcome.

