Randomization stratified by asthma severity and study site with each stratum in randomly allocated block sizes of two using the ralloc program in Stata^{82, 83} was determined most appropriate treatment assignment procedure as it will control for the majority of confounds including disease severity, location, prior conditions, race, gender etc. Procedures for the maintenance of trial randomization codes and maintaining appropriate masking for the study have been discussed in Section 6.2.3.

In total, the study will recruit 254 participants, 127 from each of the sites. The specific recruitment goals stratified by study site and asthma severity (mild, moderate or severe asthma) are: UMass Memorial Health Care (UMMHC): and the Miriam Hospital. Data is expected on 216 participants at study completion.

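### Site and asthma severity, the stratification factors, are not required in the ACQ model; if they predict ACQ, an analysis that omits them reports too wide a standard error and a conservative test

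*Combined protocol and SAP*

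**What the plan says.** Section 9.2 sets the allocation: "Randomization stratified by asthma severity and study site with each stratum in randomly allocated block sizes of two". It gives control of disease severity and location among the reasons. The Précis and section 11.2 describe the same scheme.

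Section 9.6 sets the analysis:

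- It begins with descriptive summaries and a between-arm test, a t-test where the outcome is normally distributed.
- It then adds a mixed model. The only fixed effect named as required is the arm indicator. Patient and physician random effects are also planned, and a class random effect is to be tested.
- On covariates it says: "We will estimate the intervention effects with and without adjusting for patient socio-demographic and clinical co-variables". Neither estimate is called primary.
- The rule for choosing covariates has three alternatives. The first is "Covariate adjustments will focus co-variables that are unbalanced between the two arms". The second admits covariates that substantially reduce the variance of the effect estimate. The third admits covariates that modify the effect.

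Site and severity are not named as model terms. Severity appears in 9.6 only as an example of a subgroup factor. The secondary outcomes are to be analysed in broadly the same way as the primary.

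**The concern.** Stratified allocation takes differences between strata out of the arm contrast. A model with no terms for the strata still counts those differences as residual error. If the strata predict the outcome, the standard error it reports is larger than the true sampling error of the estimate, and part of the precision gained by stratifying is lost.

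The covariate rule does not settle the matter. Blocks of two within site and severity all but rule out a visible imbalance on either factor, so the first criterion passes over them. Whether they enter then depends on two criteria that are applied after the data are seen and have no stated cut-off. At stake are the precision of the primary comparison and one avoidable analyst choice in its model.

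**Working it through.** **Inputs from section 9.2.** Alpha and power: "method at 5% significance level and at least 80% power" (taken as two-sided). Means and SD: "are 1.24 (0.66) and 1.49 (0.66) averaged over the three follow-up time points", a difference of 0.25. Correlations: "a serial correlation of 0.45 within patients" and, for physicians, "we conservatively assumed a modest within physician correlation of 0.05". There are 12 physicians per site with 9 patients each, and 108 evaluable patients per arm.

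**Reproducing the trial size.** Read 0.66 as the SD of the three-visit average.

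- ANCOVA factor: 1 − 0.45² / ((1 + 2 × 0.45)/3) = 0.680
- Design effect: 1 + (9 − 1) × 0.05 = 1.40
- Effective SD: 0.66 × √(0.680 × 1.40) = 0.644
- n per arm: 2 × 0.644² × (1.960 + 0.842)² / 0.25² = 104.2, so 105 against 108 stated
- SE at 108 per arm: 0.644 × √(2/108) = 0.0876
- Power: Φ(0.25/0.0876 − 1.960) = 81.4%

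The stated power is met without any stratification term. Other readings of the SD give other power figures, but the SE ratio and type I error below depend only on R².

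**Effect of omitting the factors.** Let R² be the share of the remaining ACQ variance that site and severity explain. The documents give no value, so a range is assumed. With the strata balanced, and taking 80% as the nominal power without the factors:

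- Excess in the reported SE: 1/√(1 − R²) − 1
- Type I error when omitted: 2 × (1 − Φ(1.960/√(1 − R²)))
- Power when omitted: Φ(0.8416/√(1 − R²))
- Power when included: Φ(2.8016/√(1 − R²) − 1.960)

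| Assumed R² | SE too wide by | Type I error, omitted | Power, omitted | Power, included | Gain (points) |
|---|---|---|---|---|---|
| 0 | 0% | 5.0% | 80.0% | 80.0% | 0 |
| 0.05 | 2.6% | 4.4% | 80.6% | 82.0% | 1.4 |
| 0.10 | 5.4% | 3.9% | 81.3% | 84.0% | 2.7 |
| 0.15 | 8.5% | 3.4% | 81.9% | 86.0% | 4.0 |

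The power of the analysis that omits the factors also rises with R², because its estimate varies less than its standard error implies. The gain must be measured from that figure, not from 80%. Starting from the reproduced 81.4%, the gain is similar: 82.0% to 83.3% at R² = 0.05, and 82.7% to 85.2% at 0.10.

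**Checks by simulation.**

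- *254 randomised in blocks of two by site and severity, 15% random dropout, no baseline covariate.* Severity never reached p < 0.05 for imbalance. At R² = 0.20 the unadjusted SE averaged about 0.090 against a true SD of about 0.083, a ratio of 0.090/0.083 = 1.08. The formula gives 1.118 for exact balance. Type I error was about 3% unadjusted and about 5% adjusted. Power rose from about 80–82% to 86–87%. At R² = 0 the two analyses had practically the same SE.
- *24 physicians with 9 patients each, within-physician correlation 0.05, physician random effect fitted, 300 runs.* With site explaining an assumed 5% or 10% of variance, leaving site out widened the SE by about 0.8% or 1.3%, against 2.6% or 5.4% by formula.

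**The case against.** The strongest reply is that the covariate rule already provides the remedy. Its second criterion admits covariates that reduce the variance of the effect estimate. If the factors matter for the standard error, that criterion can bring them in; if they do not, little is lost. Severity could also enter under the third. This stands in part. A reader who stops at the imbalance criterion might infer that the rule shuts the factors out, or admits them only by chance. The full sentence in 9.6 does not support that. But the second and third criteria govern only the adjusted estimate. They leave the t-test and the model without covariates as they are, and they choose terms from the trial data, partly by their effect on the precision of the arm contrast. The rule also speaks of patient socio-demographic and clinical variables, and site is arguably neither.

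A second reply is that planned terms already absorb some of this variance. That also stands. Physicians sit within sites, so their random effects take up much of any site difference in the mixed model. Baseline ACQ, if used as the ANCOVA in 9.2 suggests, may take up part of severity, although 9.6 does not name it as a covariate. The physician effects are not designed to absorb patient-level severity, and the t-test has neither term.

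A third reply is that the stated power is met without these terms. The closest reproduction agrees, so this is not a failure of the sample size.

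**Conclusion.** The point holds as one of precision and prespecification. Two factors that restrict the allocation are not fixed in the analysis. The t-test and the model without covariates do not include them, and the adjusted model includes them only if the analyst so decides.

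A reader might go further and infer that the standard error is too wide as a matter of fact. The documents do not show that: it depends on an R² they do not give, and at zero there is no excess. Over an assumed 0 to 0.15 the excess runs from 0% to about 8.5%, and the gain in power from 0 to about 4 points. These figures assume balanced strata and a normal approximation. They are upper figures for the mixed model, for the reasons given under the objection. Nor is there ground to infer bias or an inflated type I error; the error, if any, is on the conservative side. The change is worth making because it costs almost nothing and removes a data-dependent choice.

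**What to change.** In section 9.6, prespecify site (2 levels) and asthma severity (mild, moderate, severe) as fixed effects in every ACQ model used for inference, including the one called unadjusted, and in the secondary-outcome models that follow it. State that the three-part covariate rule applies only to other covariates, and that the t-test is descriptive.

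The cost is about one sentence and 3 degrees of freedom (1 for site, 2 for severity). Both variables are fixed before randomisation, so no new data are needed. Cohort also restricts the allocation (Précis, section 11.2); whether it needs a term is a separate decision.

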4. SELECTION AND ENROLLMENT OF STUDY PARTICIPANTS

4.1 Inclusion Criteria: To be included in the study, patients must meet the following criteria:

- Age 18 and older
- Diagnosis of asthma for greater than 12 months documented by a pulmonologist or board-certified allergist; or diagnosis of asthma for greater than 12 months documented by another type of provider that also includes an objective indicator of bronchial hyper-responsiveness (positive methacholine challenge test or $\geq 12\%$ improvement in FEV₁ or FVC in response to bronchodilator);
- Meets criteria for mild, moderate or severe asthma;^{1, 2}
- Treatment with inhaled corticosteroids for at least 3 months with stable dosing for greater than 1 month;
- Able to read and understand English, and complete informed consent process and study data collection procedures.

4.2 Exclusion Criteria: Candidates meeting any of the following will be excluded from study participation:

- Currently smoking combustible tobacco, or smoked combustible tobacco in the past year;
- Other lung diseases besides asthma (e.g., pulmonary hypertension, cystic fibrosis, COPD-emphysema, bronchiectasis, chronic bronchitis, lung cancer);
- Unable to undergo spirometry;
- Active cancer, except non-melanoma skin cancer; Currently receiving treatment for symptomatic cardiovascular disease (including congestive heart failure, unstable angina, have chest pain or had myocardial infarction or heart attack within past 6 months);
- Current or recent (within the past 3 months) severe exacerbation of asthma requiring hospitalization or oral glucocorticoids;
- Currently pregnant or planning to become pregnant in the next 18 months (due to change in asthma course and confounding effects of physiologic gestational dyspnea on symptoms);
- Hospitalized for a psychiatric or mental health concern in the last 2 years;
- Has taken the MBSR program in the past, and/or currently practicing meditation, or yoga that includes a meditative component, at least weekly for the past 2-3 months.

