6.2 Description of Evaluations and Schedule

Each of the study evaluations are described in the following table, together with time point at which they are administered.

Construct/Function	Measures	Evaluation Time Points			
		BL	6m	12m	18m
Primary Outcome Asthma Control	Asthma Control Questionnaire (ACQ) ³ is a validated 7-item multi-component measure that assesses the 5 asthma symptoms considered most important and most used by clinicians for evaluating asthma control, along with use of short-acting beta-agonist and FEV ₁ percent predicted. Patients recall their symptoms and short-acting beta-agonist use during the previous week; FEV ₁ is obtained from spirometry. Questions are scored on a 7-point scale (0=good control, 6=poor control), and the overall score (range 0-6) is the mean of the seven responses. Changes of 0.5 or greater in the score are considered important differences. ⁸⁵	■	■	■	■
Secondary Endpoints					
Symptoms, Symptom-free days	Asthma Control Diary ³ completed daily for 2 weeks at each assessment point provides daily asthma symptoms and the proportion of symptom-free days per week. For comparison to the ACQ results, diary information will be combined with lung function data in order to categorize the level of asthma control according to 2012 GINA guidelines, with the categorical variables being controlled, partly controlled, and uncontrolled.	■	■	■	■
Medication Use	Both controller and reliever medication use will be documented daily during the 2-week assessment period. In addition, controller medication	■	■	■	■

	dose and frequency of use will be obtained from electronic prescription data. Prescription fills will be identified through pharmacy claims data as described in prior studies. ⁸⁶ These data identified more than 99% of all inhaled corticosteroids (ICS) prescriptions filled by health plan members. ⁸⁷ Adherence is estimated as the number of days' supply for each fill divided by the total number of days between the present fill and the subsequent ICS fill. Periodic adherence estimates will be assessed and a final overall mean measure of adherence is then calculated based on the percentage of ICS adherence for each interval.				

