Secondary Outcomes: Analytic approaches for asthma-related QoL, respiratory interoceptive accuracy, lung function are generally similar to those for the two primary outcomes. To test the mediation effect of respiratory interoceptive accuracy (RIA) on asthma control, QoL, and medication use, we will first compare the difference in RIA by treatment arm. We will then use difference-to-difference approach to analyze the longitudinal associations of the changes in RIA from baseline to each follow-up time point with changes in ACQ, QoL and medication use from baseline to comparable follow-up time points.¹⁰¹⁻¹⁰³ Since we will have measures on three follow-ups, we will use linear mixed models where ACQ, QoL and medication use are treated as outcomes, RIA as the primary predictor, with and without an interaction term between RIA and MBSR indicator. These analyses will help answer whether MBSR intervention improved RIA, and whether between treatment differences in RIA would explain the observed differences in ACQ, QoL and medication use. We will compute incremental cost-effectiveness of MBSR compared with HLC as the difference in average health care costs per study participant over 18 months between MBSR and HLC, divided by the difference in average ACQ. As planned for another NIH-funded cost-effectiveness study (5R01AA009892-19), we will use the overlap between self-reported and administrative reimbursement data to estimate models of administratively estimated inpatient, outpatient, and medication services data as functions of the self-reported data. We will apply these models to all self-reported data to derive the 18-month health care costs of MBSR and HLC. We will calculate the cost of delivering the MBSR and HLC from the Brief Treatment Cost Analysis Tool (TCAT), a validated costing tool for counseling interventions.⁸⁹ Sensitivity analysis: ICER ratios will be computed between baseline and active comparator, with usual considerations of uncertainty evaluated in a probabilistic sensitivity analysis to determine the level to which our cost-effectiveness conclusions are robust.

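### The cost-effectiveness ratio uses raw between-arm differences with no stated baseline adjustment, ACQ direction or time point, and its sensitivity version is not clearly MBSR versus HLC

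*Combined protocol and SAP*

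**What the plan says.** Secondary objective 4 (section 1.2) asks whether MBSR is more cost-effective than HLC by 18 months. Section 9.6, under secondary outcomes, makes the ratio "the difference in average health care costs per study participant over 18 months between MBSR and HLC, divided by the difference in average ACQ". The scale of the denominator is set in the measures table of section 6.2: "Questions are scored on a 7-point scale (0=good control, 6=poor control", so lower is better.

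On robustness, section 9.6 says that "ICER ratios will be computed between baseline and active comparator" and refers to a probabilistic sensitivity analysis. It names no interval method, net-benefit measure or willingness-to-pay range. A later paragraph of 9.6 describes the comparison between the arms as incremental cost per unit of added clinical benefit.

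The section 6.2 table schedules both the ACQ and health care use and cost over the prior 6 months at baseline and at 6, 12 and 18 months.

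**The concern.** There are three gaps.

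1. **Raw differences.** The ratio is written as a difference in means over a difference in means. Section 9.6 allows covariate adjustment in the ACQ models but does not carry it into the ratio, and it states no baseline adjustment for the cost difference.
2. **Undefined denominator.** The plan does not say which arm is subtracted from which, at which visit or visits, or whether ACQ enters as a level or as a change. The sign of an ICER carries its meaning, so two analysts following the text could report opposite signs. A ratio also behaves badly when its denominator is close to zero, and the plan names no other basis for inference.
3. **Sensitivity contrast.** Neither baseline nor active comparator is defined, and the pair does not match the MBSR-versus-HLC contrast used in section 1.2 and in the rest of 9.6.

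At stake is whether secondary objective 4 gets a reproducible answer that rests on the randomisation.

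**Working it through.** **Inputs.** From section 9.2: "the mean (SD) of ACQ scores for the MBSR and HLC groups are 1.24 (0.66) and 1.49 (0.66"), 108 per arm, serial correlation 0.45, within-physician correlation 0.05 and 9 patients per physician. The test is "at 5% significance level and at least 80% power"; I take the 5% as two-sided. The documents give no cost difference.

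**Plan's own figures.** 1.49 − 1.24 = 0.25, which matches "the trial can detect an intervention effect of 0.25 ACQ score improvement". A plain two-sample comparison of 108 per arm with SD 0.66 has power 0.795. ANCOVA on the three-visit average gives 0.989, or 0.948 with the physician design effect 1 + (9 − 1) × 0.05 = 1.4. The stated power holds.

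**Direction.** MBSR minus HLC is 1.24 − 1.49 = −0.25. HLC minus MBSR is +0.25. For illustration, assume a cost difference of 500 in either direction:

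| MBSR cost minus HLC cost | Divided by −0.25 | Divided by +0.25 |
|---|---|---|
| +500 | −2000 | +2000 |
| −500 | +2000 | −2000 |

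The order of subtraction changes the sign but not the size.

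**Near-zero denominator.** A Fieller interval for a ratio is unbounded exactly when the denominator's own interval includes 0. I take 0.66 as the SD at one visit and the correlation as equal across all visits. Then SE = 0.66 × √(f × D × 2/108), with D = 1 or 1.4 and f as follows:

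- three-visit average, adjusted for baseline: (1 + 2 × 0.45)/3 − 0.45² = 0.4308
- three-visit average, raw: (1 + 2 × 0.45)/3 = 0.6333
- one visit, adjusted: 1 − 0.45² = 0.7975
- one visit, raw: 1

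P(interval includes 0) = Φ(1.96 − δ/SE) − Φ(−1.96 − δ/SE), and P(wrong sign) = Φ(−δ/SE), where δ is the true effect. Ranges run from D = 1 to D = 1.4. The effect of 0.10 is my assumption.

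| ACQ difference | SE | Includes 0, δ = 0.25 | Includes 0, δ = 0.10 | Wrong sign, δ = 0.10 |
|---|---|---|---|---|
| Three visits, adjusted | 0.059–0.070 | 1–5% | 60–70% | 5–8% |
| Three visits, raw | 0.071–0.085 | 6–16% | 71–78% | 8–12% |
| One visit, adjusted | 0.080–0.095 | 12–25% | 76–82% | 11–15% |
| One visit, raw | 0.090–0.106 | 20–35% | 80–84% | 13–17% |

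**Gain from adjustment.** On these inputs, adjusting for baseline ACQ cuts the variance of the ACQ difference by 1 − 0.4308/0.6333 = 32% for the three-visit average and by 0.45² = 20% for one visit. The gain for cost cannot be computed because the documents give no correlation between baseline and follow-up cost.

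**Sensitivity sentence.** Elsewhere in the plan, baseline is the assessment before randomisation, and section 2.2 calls HLC an active control. On that reading the contrast is before versus after within HLC, and MBSR drops out. The cost windows would also differ: 6 months at baseline against 18 months in the main ratio. If baseline instead means a reference strategy, the plan does not say which one.

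**The case against.** A reader might infer that the ratio is stated with its sign reversed. The text does not show that. In the definition, the phrase naming the two arms is attached to cost. The denominator is only "divided by the difference in average ACQ", with no order. Section 9.2 words the effect as a positive improvement, and the later paragraph of 9.6 speaks of added benefit. Both lean towards a benefit-positive denominator. The coding MBSR = 1 in 9.6 would give a negative coefficient, but it belongs to the mixed models and does not define the ratio. The direction is therefore unspecified, not shown to be wrong.

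A reader might also infer that baseline has replaced HLC in the sensitivity analysis. That is one reading of undefined terms. HLC may itself be the active comparator, and the same sentence is meant to test conclusions about MBSR versus HLC.

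A third inference is that costs must rise after entry, because section 4.2 excludes "Current or recent (within the past 3 months) severe exacerbation of asthma requiring hospitalization or oral glucocorticoids". The documents hold no cost data to support this, and a rise common to both arms would cancel in the randomised difference.

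Finally, a probabilistic sensitivity analysis is already planned, and a protocol need not name every health-economic method for a secondary objective. That is fair. It does not supply the missing baseline adjustment or the definition of the denominator, and it does not say which contrast the sensitivity analysis tests.

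**Conclusion.** The point holds as a gap in specification with a cost in precision, not as a demonstrated error of sign. The cost-effectiveness ratio is set out as raw differences although baseline values are available. Its denominator lacks a direction and a time point, and its sensitivity contrast does not match the randomised comparison as worded.

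With baseline adjustment and the planned effect of 0.25, the ratio would lack a bounded interval in about 1–5% of trials for a three-visit average and 12–25% for one visit. At an assumed 0.10 the range over both is about 60–82%. Taking the differences raw, as the definition reads, raises these to 6–16%, 20–35% and 71–84%. So the problem is modest if the planned effect is real and ACQ is averaged over visits, and serious if the effect is smaller.

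These figures rest on 0.66 being a one-visit SD, equal correlations of 0.45, a two-sided 5% level and a design effect between 1 and 1.4. Only secondary objective 4 is affected; the primary analysis and the sample size are not.

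**What to change.** Amend the cost-effectiveness text of section 9.6:

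1. Estimate the between-arm cost difference adjusted for baseline 6-month cost, and the ACQ difference adjusted for baseline ACQ.
2. Define effect as ACQ improvement, HLC minus MBSR, and state the time point (18 months, or the average over the three follow-up visits).
3. Base inference on incremental net benefit, with bootstrap intervals and an acceptability curve over a stated willingness-to-pay range. Keep the ICER as a descriptive figure.
4. Restate the sensitivity ICER and the probabilistic sensitivity analysis as MBSR versus HLC.

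The cost is a change of wording in the analysis plan and some programming. The baseline ACQ and cost data are already scheduled for collection.
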